This is a 5-year study to evaluate the effect of a 10-week patient-partner telephone-based cognitive behavioral stress management (PP-T-CBSM) intervention on chronic fatigue syndrome (CFS) symptoms in 150 CFS patients and their partners. Because many patients with CFS are unable to attend intervention sessions in clinical settings due to unpredictable periods of debilitating fatigue and limited mobility, we created a form of CBSM intervention that is delivered at the participant's home through a telecommunications system (Telephone-based CBSM) T-CBSM. A unique aspect of T-CBSM is that it uses the phone to convene groups of individuals in their homes—thus it retains some of the supportive elements of a group-based intervention. We have observed that over a 5 month period this patient-focused T-CBSM intervention is associated with decreases in CDC-based CFS symptoms and decreases in the pro-inflammatory cytokines and increases in anti-inflammatory cytokines. Greater decreases in pro-inflammatory cytokines were associated with greater increases in the negative pitch of the AM-PM slope of salivary cortisol and greater decreases in CFS symptoms. This supported our neuroimmune model as an explanation for the effects of T-CBSM on CFS symptoms. We also conducted subgroup analyses comparing partnered and unpartnered CFS patients and found that the effects of the intervention were much larger in the partnered group. We have designed a study to follow up on these findings by testing a newly designed partner-patient dual focus videotelephone-delivered CBSM intervention (PP-T-CBSM) that allows the partner to learn stress management techniques with the patient in a group format and to then practice together a set of stress management techniques such as relaxation and cognitive, behavioral and interpersonal skills training. We will compare changes in CFS symptoms, neuroimmune indicators, and psychosocial (patient and partner) functioning in participants assigned to PP-T-CBSM vs an attention time-matched telephone-based health information (T-HI) control condition in a 2 X 3 randomized experimental design with group (PP-T-CBSM, n=75 vs. T-HI, n=75) as the between-group factor, and time (Pre-intervention, 5- and 9-month follow-up) as the within-group factor.

PRIMARY AIM

AIM 1: To determine if PP-T-CBSM intervention improves CFS defining symptoms relative to participants in the T- HI condition.

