
Intervention Protocol:

After participants complete the interviews, and chronic fatigue patients complete the collection of saliva and blood, they will open an envelope that will advise them of the group they were randomly assigned to (PP-T-CBSM or T-HI). Participants who live outside our catchment area will be contacted to inform them of their randomization group. Randomization will occur in waves of eight, four dyads will be randomized to PP-T-CBSM and 4 to P-HI). Subjects randomized to PP-T-CBSM will receive 10 weeks of group intervention as described herein. A total of 4 dyads (CFS patient and their identified partner) will meet once weekly by videophone for approximately a one hour session at a mutually convenient set time. The content of the PP-T-CBSM protocol will comprise two broad domains: Cognitive, behavioral and interpersonal skills training and relaxation/imagery. The Cognitive, Behavioral and Interpersonal skills component presents information concerning stressors and stress responses from a biopsychosocial perspective. The initial 5 weeks emphasize: (1) the importance of appraisals in the stress response and in symptom occurrence; (2) understanding automatic thoughts and cognitive distortions; (3) identifying and monitoring automatic thoughts; (4) disputing and restructuring cognitive distortions into more rational thoughts, and (5) learning adaptive problem-focused and emotion-focused coping skills. By monitoring automatic thoughts associated with negative emotions, participants increase their awareness of cognitive appraisals that precede changes in emotion. Stressors of primary importance in this study are those concerning the physical symptoms of CFS and the losses associated with the illness. Participants learn how automatic thoughts, including cognitive distortions may contribute to symptom magnification and ensuing feelings of loss of perceived control. The remaining 5 weeks focus on

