Subjects randomized to Telephone Health Information (T-HI) condition will receive 10 weeks of individual telephone sessions of approximately one hour. This control condition is designed to provide equal amounts of attention and contact time without any active treatment (CBSM) being given. T-HI is designed to control for common factors such as attention, supportiveness, empathy and enthusiasm. Social support processes (e.g., group cohesiveness) are an "active ingredient" in the T-CBSM intervention and social support changes will be tested as part of our hypothesized model. By providing T-HI in an individual format, we are controlling for facilitator's time and attention, supportiveness, and empathy, but we retain the ability to test whether a supportive group intervention facilitates better quality of life and health outcomes. If we were to provide T-HI in a group format, we would be equalizing the groups on a factor that we are actually aiming to test. Moreover, once a group is assembled, it is very difficult to deter social processes as they may occur within the group or as part of ancillary group contact. The sessions cover the benefits of titrated physical and leisure activity, sleep, and proper nutrition (e.g., balanced diet, nutrition guidelines for adults), and the importance of receiving regular medical care and follow-up. Participants will be encouraged to ask questions and to discuss material at a personalized level to increase its relevance (e.g., asked to complete dietary log to increase awareness of eating habits; monitor physical activities; etc.). The material presented will be comprised of information that is commonly available and is designed to complement the ongoing medical care that participants receive from their medical treatment provider(s). Each session consists of a didactic presentation of the topics and activities to promote discussion. Patients report that they find the material to be useful. Participants will receive a Participant Workbook, which contains a summary of the information presented in each individual session and health resources. In addition, participants will be encouraged to inform their provider(s) about their study participation and to consult with provider(s) before initiating any health behavior changes (e.g., increasing physical activity). In addition to printed materials, participants will have access to system with recorded T-HI information. Usage of the system will be monitored as an indicator of dose.

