Participants will incur no appreciable physical risks through participation in this study, though they may undergo psychological discomfort at some time points. During the psychosocial intervention, participants will be given specific CFS-related information, as well as be asked to participate in assessment of sensitive topics that may lead some to experience transient and mild anxiety. In addition, some participants are likely to manifest symptom increases from time to time throughout the longitudinal component of the study, and some may experience affective distress. In these cases, every attempt will be made to provide relief and to ameliorate the source of the discomfort. Should participants experience extreme acute or persisting affective reactions at any point during the study period, they will be referred to a psychiatrist or clinical psychologist associated with the site for care. In the event that a participant reports symptoms or concerns of extreme distress (e.g., severe symptoms of depression and/or anxiety suggesting clinical concerns, suicidality, etc.), our interventionists will directly target such symptoms and assess the severity of such distress within the group context while maintaining the group process and eliciting support from other participants. Subsequent to the intervention session, the participant will be contacted individually by one of the interventionists for a more comprehensive assessment of distress. If it is determined at that point that the participant needs individual care, our interventionists and research staff will

be prepared to refer the patient to a source of clinical intervention other than our PP-T-CBSM intervention (a list of referrals will be available). Similarly, should participants experience extreme, acute or persisting affective reactions at any other point during the study period (e.g., assessment, individual contact), they will be referred to the appropriate channels within the UM Department of Psychiatry or Psychology, as well as to a list of community resources/catchment sites in the South Florida area prepared to deliver resources to deal with extreme distress. Similar procedures will be followed for participants in our T-HI condition. The information obtained in this project will help in the development of strategies for promoting quality of life among individuals living with CFS. All participants will receive fair compensation for the time they invest in completing the research protocol.

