All recruitment personnel will be trained in study procedures including the treatment of human subjects and will be required to complete the CITI certification program, which covers issues pertaining to coercion. Activities of the recruitment personnel will be monitored on a weekly basis by the Project manager with oversight by the PI. There is the potential for undue influence. Thus, all study personnel will undergo training on how to approach potential participants. There will also be a telephone script developed to insure that the information on the study is consistent and clear.

6.4. * Are there specific criteria to prematurely end a particular subject's participation in the study (e.g., predetermined safety endpoints, unexpected clinically significant findings, distress or serious adverse events, etc.)?

Select one
 Yes
 No
 Not Applicable

6.4.A. If yes, please describe:

If the participant presents a danger to him/herself or others and requires immediate mental health services the participant will be terminated from the study. Mental health referral will be provided in these instances.

If the participant conducts him/herself in such a manner that is disruptive to other participants and/or the intervention process he/she may be terminated from the study since the procedures require interactions among group participants on a regular basis and these interactions constitute an element of the intervention. Termination due to the development of a serious medical condition will be handled on a case-by-case basis in consultation with the study physician.

6.5. * Will subjects be remunerated for their participation in the study in any way other than credit toward a course requirement?

☒ Yes ☐ No

6b. Remuneration

6.5.A. * List type, frequency, interval, and total value of remuneration:

Type of Remuneration	Frequency	Total Value
View Gift Certificates	3	150 (50X3)
View Parking	3	15 (5X3)
View Gift Certificates	3	150 (50X3)

6.5.B. * If a subject withdraws from the study early, will remuneration be prorated?
no

6.5.B.(i) If yes, describe plan for prorating payments and ensure that this plan is defined in consent forms:

6.5.B.(ii) If no, justify why prorated payment is not being offered:

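### Section 6.4.A ends study participation rather than sessions only, with no stated follow-up or as-randomised analysis; its disruption rule risks somewhat more outcome loss in PP-T-CBSM

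*Combined protocol and SAP*

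**What the plan says.** Section 6.4 asks for criteria that end a subject's participation in the study early. Section 6.4.A answers with two rules relevant here.

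- **Danger (mandatory).** A participant who is a danger to self or others and "requires immediate mental health services the participant will be terminated from the study".
- **Disruption (discretionary).** A participant may be removed for conduct that is "disruptive to other participants and/or the intervention process he/she may be terminated from the study since the procedures require interactions among group participants". The reason added is that "these interactions constitute an element of the intervention".

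A serious medical condition is left to case-by-case decision and is not at issue.

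The arms differ in how sessions are delivered (section 4.4, Intervention Protocol). In PP-T-CBSM, "A total of 4 dyads (CFS patient and their identified partner) will meet once weekly by videophone". Subjects in T-HI "will receive 10 weeks of individual telephone sessions of approximately one hour", and the choice is deliberate: "By providing T-HI in an individual format, we are controlling for facilitator's time and attention". On severe distress, section 4.7 describes assessment, individual contact and referral, and adds: "Similar procedures will be followed for participants in our T-HI condition".

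The Follow-up Interview Protocol in section 4.4 has staff contact participants for the 5-month assessment once the 10-week programme is complete. Section 4.12 names repeated-measures procedures by random assignment. It states no intention-to-treat set and no method for missing outcomes.

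**The concern.** Ending sessions is a decision about delivery. Ending study participation also ends outcome measurement. When the second follows automatically from the first, events after randomisation decide whose 5- and 9-month outcomes exist.

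Two features make this more than ordinary attrition. First, the reason given for the disruption rule applies to one arm only: a T-HI participant has no fellow participants in the session to disrupt, so the opportunity for removal is unequal. Second, being a danger, or disruptive in a group, may be related to the stress, depression and social disruption measures of Hypothesis 3.1, so the missing values need not resemble the observed ones.

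At stake is the comparison of the arms as randomised. An outcome that was never sought cannot be recovered, and the plan gives no rule for handling its absence.

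**Working it through.** **Reading the text**

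1. *What ends?* The question in 6.4 and both rules in 6.4.A refer to the study, not to sessions.
2. *Does anything restore follow-up?* The Follow-up Interview Protocol ties contact to completing the programme, so someone removed in week 4, for example, has no described route to the 5- or 9-month assessment. No other available section supplies one.
3. *Does the analysis cover it?* Section 4.12 does not say how incomplete records enter. Section 4.4 (Study Procedures) separately drops from analysis any patient diagnosed with an excluded condition during the study, so analysis of everyone randomised cannot be presumed.
4. *Is the route arm-related?*

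| Rule | Force | Stated ground | PP-T-CBSM | T-HI |
|---|---|---|---|---|
| Danger | mandatory | danger and need for immediate care | applies | applies |
| Disruption, other participants | discretionary | group interaction | applies | no group in session |
| Disruption, intervention process | discretionary | group interaction | applies | could apply |

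Only the second row clearly differs by arm.

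**Size, for illustration**

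The documents give no number of terminations, and no alpha, power, effect size or SD, so the sample size cannot be reproduced. The inputs they do give are:

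- Allocation, from the opening summary: "group (PP-T-CBSM, n=75 vs. T-HI, n=75) as the between-group factor".
- Anticipated retention at T3, from section 4.4 (Study Design): 124 of 150, or 124/150 = 82.7%. That allows 26 losses (17.3%), with no split by arm or cause.
- Expected completers, from section 5.2.C: 255 of 300 persons, or 85%. This equals 127.5 dyads, close to 124.

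Assume that k PP-T-CBSM patients and no T-HI patients are removed, and that they would have scored g SD worse than the rest of their arm. The observed arm mean then shifts by

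bias = (k/75) × g.

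| k | share of 75 | g = 0.5 | g = 1.0 |
|---|---|---|---|
| 1 | 1.3% | 0.007 SD | 0.013 SD |
| 2 | 2.7% | 0.013 SD | 0.027 SD |
| 4 | 5.3% | 0.027 SD | 0.053 SD |
| 8 | 10.7% | 0.053 SD | 0.107 SD |

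With 62 as the denominator (124/2, the number per arm expected at T3), k = 2 to 4 gives 2/62 × 0.5 = 0.016 to 4/62 × 1.0 = 0.065 SD. If those removed would have scored better than the rest, every sign reverses.

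**Scale.** Assuming a two-sided 5% test and 80% power, 62 per arm detects (1.960 + 0.842) × √(2/62) = 0.503 SD. The 0.053 SD case is about a tenth of that (0.053/0.503 = 0.106). At a true difference of 0.5 SD, power is 79.5% with 62 vs 62, 78.2% with 58 vs 62, and 76.6% with 54 vs 62. Lost power is not the issue; possible bias is.

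**The case against.** The strongest reply is that the text claims less than a worried reader may infer, and that the numbers are small.

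A reader might infer that outcomes *are* lost selectively from the intervention arm. The documents do not support that. Termination for disruption is discretionary, no frequency is given, and disturbing the intervention process is possible in a one-to-one T-HI session. What stands is an unequal opportunity and a rationale that fits one arm.

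A reader might also count the danger rule as arm-selective. It names no arm, and section 4.7 applies similar distress procedures in T-HI. Entry criteria exclude psychoses, substance dependency and current suicidal thoughts, and section 4.7 describes assessment and referral for distress, so such terminations are plausibly few. If PP-T-CBSM reduces distress as hypothesised, this rule could remove more T-HI patients and bias the comparison *against* PP-T-CBSM.

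Nor do the documents show that any loss favours PP-T-CBSM, or that it affects the primary outcome. That outcome is total CDC-based symptoms, and nothing links disruptive conduct to worse symptom scores. Nor are terminations shown to be losses beyond the 26 already allowed for.

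Finally, with two to four cases a worst-case sensitivity analysis could bound the effect, and the consent forms, which were not available for review, may address contact after termination. Both points are fair. But a bound does not replace an outcome that could have been collected, and the plan specifies no such analysis.

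**Conclusion.** The point holds as a gap in the plan with a risk attached. As written, 6.4.A ends study participation under both rules, and the available text neither continues assessment nor commits to analysing these patients as randomised. The disruption rule carries a risk of more outcome loss in PP-T-CBSM. The danger rule can cause outcome-related loss without favouring either arm by its wording.

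The size and direction of any bias are unknown. The 0.013 to 0.053 SD range rests wholly on assumptions: 2 to 4 removals, none in T-HI, and a difference of 0.5 to 1 SD. It is probably small unless terminations are frequent. The case for acting rests on low cost and on the fact that uncollected outcomes cannot be retrieved, not on a large expected distortion.

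**What to change.** In section 6.4.A, separate the end of sessions from the end of follow-up. When sessions are ended under that section:

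- record the date and the reason;
- offer the 5- and 9-month online questionnaires, and the saliva and blood samples, where the person is willing;
- analyse the patient in the arm assigned at randomisation, and say so in section 4.12 together with how missing outcomes are handled;
- report terminations by arm and reason.

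State also whether terminating a partner ends the patient's outcome collection. Sections 5.5 and 5.7 require a participating partner at entry, and the documents are silent on what follows if the partner is removed.

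The criteria for ending sessions are not in question and need no change.

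The cost is a short addition to 6.4.A and 4.12, matching consent text where it is not already there, and a few extra contacts. The questionnaires are already completed online and the saliva kits already mailed, so little new infrastructure is needed.
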